#### 5.4. Screen Failures

Screen failures are defined as participants who consent to participate in the clinical study but are not subsequently enrolled in the study. A minimal set of screen failure information is required to ensure transparent reporting of screen failure participants to meet the CONSORT publishing requirements and to respond to queries from regulatory authorities. Minimal information includes demography, screen failure details, and any SAEs.

Individuals who do not meet the criteria for participation in this study (screen failure) may be rescreened under a different participant number, once eligibility criteria are met.

# 5.5. Criteria for Temporarily Delaying Enrollment/Randomization/Administration of Study Intervention

The following conditions may allow a participant to be randomized once the conditions have resolved and the participant is otherwise eligible. Participants meeting these criteria at Visit 1 will be considered screen failures if enrollment has closed once the condition(s) has/have resolved.

• A positive influenza or SARS-CoV-2 test result (NAAT or rapid antigen test) within the previous 28 days.

- Current febrile illness (oral temperature  $\ge 38.0^{\circ}$ C [ $\ge 100.4^{\circ}$ F]) or other acute illness within 48 hours before study intervention administration.
- Receipt of any nonstudy vaccine within 28 days before study intervention administration at Visit 1.
- Anticipated receipt of any nonstudy vaccine within 28 days after study intervention administration at Visit 1.
- Receipt of short-term (<14 days) systemic corticosteroids at a dose of ≥20 mg/day of prednisone or equivalent. Study intervention administration should be delayed until systemic corticosteroid use has been discontinued for at least 28 days.
  - Note: Systemic corticosteroids administered at a dose of <20 mg/day of prednisone or equivalent are permitted. Inhaled/nebulized, intra-articular, intrabursal, or topical (skin or eyes) corticosteroids are permitted.

#### 6. STUDY INTERVENTION(S) AND CONCOMITANT THERAPY

Study interventions are all prespecified investigational and medical devices, and other interventions (eg, surgical and behavioral), intended to be administered to the study participants during the study conduct.

# 6.1. Study Intervention(s) Administered

Participants will be enrolled and randomized to each of the following vaccine groups:

- **Group 1:** BNT162b2 (Omi XBB.1.5)/RIV (as a single injection) administered in the left deltoid and placebo administered in the right deltoid
- Group 2: BNT162b2 (Omi XBB.1.5) administered in the left deltoid and RIV administered in the right deltoid
- **Group 3:** BNT162b2 (Omi XBB.1.5) administered in the left deltoid and placebo administered in the right deltoid
- **Group 4:** RIV administered in the left deltoid and placebo administered in the right deltoid

	Study Intervention(s)			
Intervention Name	BNT162b2 (Omi XBB.1.5)/RIV	BNT162b2 (Omi XBB.1.5)	RIV	Normal saline placebo
Туре	mRNA and recombinant protein vaccine	mRNA vaccine	Recombinant protein vaccine	Placebo
Use	Experimental	Comparator	Comparator	Placebo for blinding
IMP or NIMP/AxMP	IMP	IMP	IMP	IMP
Dose Formulation	Suspension for injection and Recombinant	Suspension for injection	Solution for injection	Normal saline (0.9% sodium chloride solution for injection)
Unit Dose Strength(s)	As detailed in the IPM	As detailed in the IPM	As detailed in the IPM	N/A
Targeted Influenza Strains	As recommended by WHO for cell culture or recombinant-based vaccines (2023-2024 northern hemisphere influenza season) a	N/A	As recommended by WHO for cell culture or recombinant-based vaccines (2023-2024 northern hemisphere influenza season) a	N/A
Dosage Level(s)	BNT162b2 (Omi XBB.1.5) 30 μg RIV 180 μg	30 μg mRNA	180 μg Recombinant protein	0.5 mL
Route of Administration	Intramuscular injection	Intramuscular injection	Intramuscular injection	Intramuscular injection
Sourcing	Provided centrally by the sponsor	Provided centrally by the sponsor	Provided centrally by the sponsor	Provided centrally by the sponsor

		Study Intervention(s)		
Packaging and Labeling	Study intervention will be generated by mixing the following at the site at the dose-level combinations detailed below:  • BNT162b2 (Omi XBB.1.5)  • RIV Each vial will be labeled per country requirement	Study intervention will be provided in a glass vial as open-label supply. Each vial will be labeled per country requirement	Study intervention will be provided as either a PFS or a glass/plastic vial as open-label supply	Study intervention will be provided in a plastic vial as open-label supply
SRSD	Combined IBs	IB	Flublok IB	N/A

a. For the 2023-2024 influenza season, Flublok Quadrivalent is formulated to contain 180 μg HA per 0.5-mL dose, with 45 μg HA of each of the following 4 influenza virus strains: A/West Virginia/30/2022 (A/Wisconsin/67/2022 pdm09-like virus) (H1N1), A/Darwin/6/2021 (H3N2), B/Austria/1359417/2021, and B/Phuket/3073/2013.

	Study Arm(s)			
Group	1	2	3	4
Arm Title	BNT162b2 (Omi XBB.1.5)/RIV + normal saline placebo	BNT162b2 (Omi XBB.1.5) + RIV	BNT162b2 (Omi XBB.1.5) + normal saline placebo	RIV + normal saline placebo
Arm Description	Participants will receive a single injection combination of BNT162b2 (Omi XBB.1.5) (30 µg) and RIV (180 µg) administered in the left deltoid and normal saline placebo administered in the right deltoid at Visit 1 (Day 1)	Participants will receive BNT162b2 (Omi XBB.1.5) (30 µg) administered in the left deltoid and RIV (180 µg) administered in the right deltoid at Visit 1 (Day 1)	Participants will receive BNT162b2 (Omi XBB.1.5) (30 µg) administered in the left deltoid and normal saline placebo administered in the right deltoid at Visit 1 (Day 1)	Participants will receive RIV (180 µg) administered in the left deltoid and normal saline placebo administered in the right deltoid

#### 6.1.1. Administration

Standard vaccination practices must be observed and vaccine must not be injected into blood vessels. Appropriate medication and other supportive measures for management of an acute hypersensitivity reaction must be available in accordance with local guidelines for standard immunization practices.

Administration of study interventions will be performed by an appropriately qualified, trained, and vaccine-experienced member of the study staff (eg, physician, nurse, physician's assistant, nurse practitioner, pharmacist, or medical assistant) as allowed by local, state, and institutional guidance.

Study intervention administration details will be recorded on the CRF.

Participants will receive 2 injections at Visit 1 as randomized in accordance with the SoA. Study intervention should be administered intramuscularly into the deltoid muscle of the appropriate arm as detailed in Table 3, and in such a way as to ensure that the participants remain blinded.

**Table 3.** Anatomical Location for Study Intervention Administration

Vaccine Group Number	Left Deltoida	Right Deltoid a
1	BNT162b2 (Omi XBB.1.5)/RIV	Placebo
2	BNT162b2 (Omi XBB.1.5)	RIV
3	BNT162b2 (Omi XBB.1.5)	Placebo
4	RIV	Placebo

a. Study intervention will be administered in contralateral arms. Local reactions will be assessed at the injection site on both the left and right deltoids.

#### 6.1.2. Medical Devices

RIV and normal saline placebo may be provided as a PFS, in which case the PFS should be considered a medical device.

All medical device deficiencies (including malfunction, use error, and inadequate labeling) for the medical devices listed above shall be documented and reported by the investigator throughout the clinical investigation (see Section 8.4.9) and appropriately managed by the sponsor.

# 6.2. Preparation, Handling, Storage, and Accountability

- 1. The investigator or designee must confirm that appropriate conditions (eg, temperature) have been maintained during transit for all study interventions received and any discrepancies are reported and resolved before use of the study intervention.
- 2. Only participants enrolled in the study may receive study intervention and only authorized site staff may supply, prepare, and/or administer study intervention.

- 3. All study interventions must be stored in a secure, environmentally controlled, and monitored (manual or automated recording) area in accordance with the labeled storage conditions with access limited to the investigator and authorized site staff. At a minimum, daily minimum and maximum temperatures for all site storage locations must be documented and available upon request. Data for nonworking days must indicate the minimum and maximum temperatures since previously documented upon return to business.
- 4. Any excursions from the study intervention label storage conditions should be reported to Pfizer upon discovery along with actions taken. The site should actively pursue options for returning the study intervention to labeled storage conditions, as soon as possible. Once an excursion is identified, the study intervention must be quarantined and not used until Pfizer provides permission to use the study intervention. Specific details regarding the excursion definition and information to report for each excursion will be provided to the site in the IPM.
- 5. Any storage conditions stated in the SRSD will be superseded by the storage conditions stated on the label. See the IPM for storage conditions of the study intervention.
- 6. Study interventions should be stored in their original containers.
- 7. The investigator, institution, head of the medical institution (where applicable), or authorized site staff is responsible for study intervention accountability, reconciliation, and record maintenance (ie, receipt, reconciliation, and final disposition records), such as the IPAL or sponsor-approved equivalent. All study interventions will be accounted for using a study intervention accountability form/record.
- 8. Further guidance and information for the final disposition of unused study interventions are provided in the IPM. All destruction must be adequately documented. If destruction is authorized to take place at the investigator site, the investigator must ensure that the materials are destroyed in compliance with applicable environmental regulations, institutional policy, and any special instructions provided by Pfizer.

Upon identification of a product complaint, notify the sponsor within 1 business day of discovery as described in the IPM.

#### 6.2.1. Preparation and Dispensing

See the IPM, package insert, or equivalent for instructions on how to prepare the study intervention for administration. Study intervention should be prepared and dispensed by an appropriately qualified and experienced member of the study staff (eg, physician, nurse, physician's assistant, nurse practitioner, pharmacy assistant/technician, or pharmacist) as allowed by local, state, and institutional guidance. A second staff member will verify the dispensing.

# 6.3. Assignment to Study Intervention

Allocation (randomization) of participants to study arms will proceed through the use of an IRT system (IWR). The site personnel (study coordinator or specified designee) will be required to enter or select information including but not limited to the user's ID and password, the protocol number, and the participant number. The site personnel will then be provided with a randomization number corresponding to the assigned study intervention.\* The IRT system will provide a confirmation report containing the participant number, randomization number, and study intervention allocation assigned. Confirmation report must be stored in the site's files.

\* Do not randomize until eligibility is confirmed and the participant is present.

Study intervention will be dispensed at the study visits summarized in the SoA.

The study-specific IRT reference manual and IPM will provide the contact information and further details on the use of the IRT system.

# 6.4. Blinding

This is a single-blind study.

# 6.4.1. Blinding of Participants

Participants will be blinded to their assigned study intervention.

# 6.4.2. Blinding of Site Personnel

Investigators and other site staff will be unblinded to participants' assigned study intervention.

#### 6.4.3. Blinding of the Sponsor

Sponsor staff will be unblinded to participants' assigned study intervention.

#### 6.4.4. Breaking the Blind

Not applicable.

# 6.5. Study Intervention Compliance

When participants are dosed at the site, they will receive study intervention directly from the investigator or designee, under medical supervision. The date and time of each dose administered in the clinic will be recorded in the source documents and recorded in the CRF. The dose of study intervention and study participant identification will be confirmed at the time of dosing by a member of the study site staff other than the person administering the study intervention.

#### 6.6. Dose Modification

Not applicable.

# 6.7. Continued Access to Study Intervention After the End of the Study

No study intervention will be provided to participants at the end of their study participation.

#### 6.8. Treatment of Overdose

For this study, any dose of study intervention greater than 1 dose of study intervention within a 24-hour time period will be considered an overdose.

Pfizer does not recommend specific treatment for an overdose.

In the event of an overdose, the investigator should:

- 1. Contact the study medical monitor within 24 hours.
- 2. Closely monitor the participant for any AEs/SAEs as medically appropriate and follow up until resolution, stabilization, the event is otherwise explained, or the participant is lost to follow-up (as defined in Section 7.3).
- 3. Document the quantity of the excess dose as well as the duration of the overdose in the CRF.
- 4. Overdose is reportable to Pfizer Safety only when associated with an SAE.

# 6.9. Prior and Concomitant Therapy

The following concomitant medications and vaccinations will be recorded in the CRF:

- Receipt of any COVID-19 vaccine from 12 months prior to enrollment until the last visit (Visit 3).
- Receipt of licensed or investigational influenza vaccine from 12 months prior to enrollment until the last visit (Visit 3).
- Any vaccinations received from 28 days prior to Visit 1 until the last visit (Visit 3).
- Details of any concomitant medication taken to treat fever or pain (solicited reactogenicity symptoms) as reported in the e-diary will be collected.

#### 6.9.1. Prohibited During the Study

Receipt of the following vaccines and medications during the time periods listed below may exclude a participant from the per-protocol analysis from that point onward; however, it is anticipated that the participant would not be withdrawn from the study (see Section 7). Medications should not be withheld if required for a participant's medical care.

• Unless considered medically necessary, no vaccines other than study intervention should be administered within 14 days before and 14 days after study vaccination at Visit 1.

- Receipt of any other (nonstudy) coronavirus vaccine from enrollment throughout the entire study is prohibited.
- Receipt of any other (nonstudy) seasonal influenza vaccine from enrollment throughout the entire study is prohibited.
- Receipt of chronic medications with known systemic immunosuppressant effects, or radiotherapy, within 60 days before enrollment through conclusion of the study is prohibited.
- Receipt of systemic corticosteroids (≥20 mg/day of prednisone or equivalent) for ≥14 days is prohibited from 28 days prior to enrollment through 28 days after administration of the study intervention.
- Planned receipt of blood/plasma products, immunoglobulins, or monoclonal antibodies, from 90 days before study intervention administration through conclusion of the study, is prohibited.
- Prophylactic antipyretics and other pain medication to prevent symptoms associated with study intervention administration are not permitted. However, if a participant is taking a medication for another condition, even if it may have antipyretic or pain-relieving properties, it should not be withheld prior to study vaccination.

# 6.9.2. Permitted During the Study

- Hormonal contraceptives that meet the requirements of this study are allowed to be used in participants who are WOCBP (see Appendix 4).
- Medication other than that described as prohibited in Section 6.9.1 required for treatment of preexisting conditions or acute illness is permitted.
- Inhaled, topical, or localized injections of corticosteroids (eg, intra-articular or intrabursal administration) are permitted.

# 7. DISCONTINUATION OF STUDY INTERVENTION AND PARTICIPANT DISCONTINUATION/WITHDRAWAL

# 7.1. Discontinuation of Study Intervention

It may be necessary for a participant to permanently discontinue study intervention. Reasons for permanent discontinuation of study intervention include the following: AEs; participant request; investigator request; pregnancy; protocol deviation (including no longer meeting all the inclusion criteria, or meeting 1 or more exclusion criteria).

Discontinuation of study intervention does not represent withdrawal from the study. If study intervention is permanently discontinued, the participant should remain in the study to be evaluated for safety. See the SoA for data to be collected at the time of discontinuation of study intervention and follow-up for any further evaluations that need to be completed.

In the event of discontinuation of study intervention, it must be documented on the appropriate CRF/in the medical records whether the participant is discontinuing further receipt of study intervention or also from study procedures, further study follow-up, and/or future collection of additional information.

# 7.2. Participant Discontinuation/Withdrawal From the Study

A participant may withdraw from the study at any time at their own request. Reasons for discontinuation from the study include the following:

- Refused further study procedures;
- Lost to follow-up;
- Death;
- Study terminated by sponsor;
- Reactogenicity event;
- AEs:
- Participant request;
- Investigator request;
- Select protocol deviations (eg, receipt of a COVID-19 and influenza vaccine at any time during this study).

If a participant withdraws from the study, they may request destruction of any remaining samples taken and not tested, and the investigator must document any such requests in the site study records and notify the sponsor accordingly.

If the participant withdraws from the study and also withdraws consent (see Section 7.2.1) for disclosure of future information, no further evaluations will be performed and no additional data will be collected. The sponsor may retain and continue to use any data collected before such withdrawal of consent.

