# 8.4.1. Time Period and Frequency for Collecting AE and SAE Information

The time period for actively eliciting and collecting AEs and SAEs ("active collection period") for each participant begins from the time the participant provides informed consent, which is obtained before the participant's participation in the study (ie, before undergoing any study-related procedure and/or receiving study intervention), through and including Visit 2. At Visit 3 (approximately 6 months after vaccination), the participant will be asked about AESIs since Visit 1.

Additionally, any AEs occurring up to 48 hours after any subsequent blood draws must be recorded in the CRF.

SAEs will be collected from the time the participant provides informed consent through the duration of the study (Visit 3, approximately 6 months after vaccination).

Follow-up by the investigator continues throughout the active collection period and until the AE or SAE or its sequelae resolve or stabilize at a level acceptable to the investigator.

When a clinically important AE remains ongoing at the end of the active collection period, follow-up by the investigator continues until the AE or SAE or its sequelae resolve or stabilize at a level acceptable to the investigator and Pfizer concurs with that assessment.

For participants who are screen failures, the active collection period ends when screen failure status is determined.

If the participant withdraws from the study and also withdraws consent for the collection of future information, the active collection period ends when consent is withdrawn.

If a participant permanently discontinues or temporarily discontinues from the study because of an AE or SAE, the AE or SAE must be recorded on the CRF and the SAE reported using the Vaccine SAE Report Form or via PSSA.

Investigators are not obligated to actively seek information on AEs or SAEs after the participant has concluded study participation. However, if the investigator learns of any SAE, including a death, at any time after a participant has concluded study participation, and they consider the event to be reasonably related to the study intervention, the investigator must promptly report the SAE to Pfizer using the Vaccine SAE Report Form or via PSSA.

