3. ENDPOINTS AND BASELINE VARIABLES: DEFINITIONS AND CONVENTIONS

3.1. Primary Endpoints

3.1.1. Safety Primary Endpoints

The safety primary endpoints are as follows:

- Local reactions for up to 7 days following vaccination
- Systemic events for up to 7 days following vaccination
- AEs from vaccination through 4 weeks after vaccination
- SAEs from vaccination through 6 months after vaccination

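### Protocol Sections 6.9.1 and 7.2 point in different directions on whether a participant who receives an outside COVID-19 or influenza vaccine stays in the study, and 6-month SAE follow-up could be cut short

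*Protocol*

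**What the plan says.** Protocol Section 6.9.1 prohibits two outside vaccines for the whole study: "Receipt of any other (nonstudy) coronavirus vaccine from enrollment throughout the entire study is prohibited", and "Receipt of any other (nonstudy) seasonal influenza vaccine from enrollment throughout the entire study is prohibited". Its opening paragraph says that receiving a listed product may remove the participant from the per-protocol analysis from then on; however, "it is anticipated that the participant would not be withdrawn from the study (see Section 7").

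Protocol Section 7.2 lists reasons for discontinuation from the study. One of them is select protocol deviations, and the single example given is "receipt of a COVID-19 and influenza vaccine at any time during this study".

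The endpoint exposed is a primary one. SAP Section 3.1.1 lists "SAEs from vaccination through 6 months after vaccination", and Protocol Section 8.4.1 says that "SAEs will be collected from the time the participant provides informed consent through the duration of the study (Visit 3, approximately 6 months after vaccination"). On early departure, the same section expressly closes active collection only where a participant leaves and consent to further data collection is revoked too. It also says that investigators have no duty to go looking for AEs or SAEs once a participant has finished in the study.

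SAP Section 4 defines the safety set as everyone who received at least one dose. SAP Section 6.1.1.4.1 uses that set for SAEs and imputes nothing except partial start dates.

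**The concern.** Section 6.9.1 sends the reader to Section 7 as though the two agreed, and Section 7.2 then points the other way for what is evidently the same kind of event. One site may keep such a participant to Visit 3 while another discontinues them, each with text to cite.

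The main exposure is the 6-month SAE percentage. If a participant is discontinued at, say, month 3 and nobody asks about SAEs afterwards, that person stays in the denominator with no event recorded for the remaining months. The exploratory 6-month titers would also be missing, rather than excluded under a documented rule. The 7-day reactogenicity and 4-week AE endpoints are less exposed because their windows close early.

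**Working it through.** **1. The two sections side by side**

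| | Section 6.9.1 | Section 7.2 |
|---|---|---|
| Event | A nonstudy coronavirus vaccine; separately, a nonstudy seasonal influenza vaccine | A COVID-19 *and* influenza vaccine, without the word *nonstudy* |
| Consequence | Possible exclusion from the per-protocol analysis; expected to stay in the study | Listed as a reason for discontinuation from the study |
| Strength | *Anticipated* | *Include*, *select*, *eg* |

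Neither column is a command, but the signals differ.

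**2. What the rest of the plan assumes**

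Protocol Section 6.9 records outside vaccines up to Visit 3, and Sections 8.10.2 and 8.10.3 collect them at Visits 2 and 3. SAP Section 6.6.4 tabulates vaccines given after study vaccination. SAP Section 4 gives receipt of a prohibited vaccine as an example of an important deviation affecting immunogenicity assessment. All of this fits with participants staying in follow-up. The Section 7.2 example is the outlier.

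**3. What happens to SAE data after a deviation-driven discontinuation**

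Protocol Section 8.4.1 expressly ends active collection early for someone who leaves the study only when consent is withdrawn as well. It also lifts the duty to seek SAEs once participation has concluded. It does not say which of these governs a participant discontinued for a deviation who has not withdrawn consent. Loss of SAE data is therefore possible, not automatic.

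**4. Direction of the effect**

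Let p be the true 6-month SAE percentage, d the share of a group discontinued, and q the share of those participants' 6-month SAE risk that falls after they leave. With everyone dosed in the denominator, no imputation, and discontinuation unrelated to SAE risk (an assumption), the expected reported percentage is p × (1 − d × q). The error can only be downward. For p = 1%:

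- d = 5%, q = 1: 1% × (1 − 0.05) = 0.95%.
- d = 20%, q = 1: 1% × (1 − 0.20) = 0.80%.
- d = 20%, q = 0.5: 1% × (1 − 0.10) = 0.90%.

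**5. The plan's own detection figure**

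Table 7 in Protocol Section 9.5 gives 0.80 for at least one event at a true rate of 1% with 160 participants. The formula is 1 − (1 − p)^n, and 1 − 0.99^160 = 0.7997, so the figure reproduces.

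**6. The same figure with follow-up lost**

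The documents give no rate of outside vaccination. The shares below are assumptions, and lost participants are taken to contribute nothing (q = 1).

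| Share lost | n contributing | Chance of at least one event, p = 1% |
|---|---|---|
| 0% | 160 | 0.80 |
| 5% | 160 × 0.95 = 152 | 1 − 0.99^152 = 0.78 |
| 10% | 160 × 0.90 = 144 | 1 − 0.99^144 = 0.76 |
| 20% | 160 × 0.80 = 128 | 1 − 0.99^128 = 0.72 |

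**The case against.** The best defence is that the two sections can be read together. Section 6.9.1 states a general expectation covering all listed vaccines and medications, and its pointer to Section 7 leads to selected exceptions. Section 7.2 is an open list that also contains death and loss to follow-up, so it describes why people leave and does not tell sites to remove anyone. This largely stands: a reader might infer that sites receive two opposite instructions, and the wording is too soft on both sides for that. It does not remove the problem, because the only exception named in 7.2 is the event that 6.9.1 expects to be handled by retention, and nothing tells a site when the exception applies.

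A reader might also take the literal 7.2 wording to cover Groups 1 and 2, who receive both vaccines by assignment. That reading is not sensible for an item listed as a protocol deviation. What remains is an editorial defect: the missing *nonstudy*, and an *and* that leaves a single outside vaccine unclear.

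The figures in the last table are also open to challenge. Discontinued participants stay in the safety set and any earlier SAEs still count, so treating them as absent overstates the loss. That is right, and the figures are worst-case bounds on an assumed loss rate. At 5% even the bound moves only from 0.80 to 0.78.

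**Conclusion.** The inconsistency is real and should be resolved, but it is a soft one. What is established is that the two sections give different expectations for outside COVID-19 or influenza vaccination, and that the plan does not say whether SAE collection continues after a discontinuation on that ground. Any follow-up lost this way can only lower the reported 6-month SAE percentage.

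The size cannot be derived from the documents. Under the assumed 5% to 20% loss with no follow-up contributed, the detection probability at a 1% rate falls from 0.80 to between 0.78 and 0.72, and the expected reported percentage from 1% to between 0.95% and 0.80%. Real losses would be smaller to the extent that participants were followed before leaving, or that sites kept collecting SAEs.

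A reader might go further and infer that losses will differ by group and distort 6-month comparisons, because Groups 3 and 4 each receive one vaccine only and site staff are unblinded (Protocol Section 6.4.2). The documents do not support this as a finding. Participants are blinded and all receive two injections, so differential loss is conjecture. The SAP reports 6-month SAEs and titers by vaccine group (Sections 6.1.1.4.1 and 6.4.1), and explicitly lists between-group contrasts only at 4 weeks (Sections 6.1.2.1.2 and 6.1.2.2.2). The study is descriptive throughout.

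**What to change.** 1. Reconcile Protocol Sections 6.9.1 and 7.2 so that the cross-reference leads to consistent text.
2. In 7.2, make clear that the example means nonstudy vaccines, and whether one vaccine suffices or both are needed.
3. State that such a vaccination is recorded and handled as a deviation for the evaluable immunogenicity analysis. Section 6.9.1 speaks of a per-protocol analysis, but no set of that name appears in Protocol Section 9.2 or SAP Section 4, so naming the evaluable set would help.
4. State in Section 8.4.1 that SAE and AESI collection continues through Visit 3 after such a vaccination unless consent is withdrawn. This protects the primary estimand.

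The cost is a small protocol text amendment, with whatever IRB/EC approval Section 10.1.1 requires. No visits are added, because Visit 3 is already scheduled, and outside vaccines are already recorded up to it.
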